7.2 Schedule of Assessments

Below is a list of all study procedures through the study period and the signs “X” indicate when the procedures are performed.

Scheduled visit	1	2	3	4	5	6	7	8	9	10	11/ET
Test & observations	Screening	1 st vaccination	2 nd vaccination					Month 3 follow-up ^g		Month 6 follow-up ^h	
Day	-14~-1	0	3 ^c ±1day	7 ±1day	14 ±3days	28 ±3days	35 ±3days	42 ±3days	56 ±3days	112 ±5days	196 ±15days
Clinical assessment											
Informed consent	X										
Inclusion/Exclusion Criteria	X	X									
Contraindication for second vaccination						X					
Demographics	X										
Medical history	X	X									
Physical Exam ^a	X	X	X	X	X	X	X	X	X	X	X
Vital sign	X	X	X	X	X	X	X	X	X	X	X
ECG	X	X ⁱ				X ⁱ			X		
Laboratory assessment											
HBsAg, HCV RNA, HIV antibody tests	X										
Nucleic acid test (nasopharyngeal/throat swabs)	X										
Serum antibodies (IgG) against SARS-CoV-2	X										
Lab (Safety)											
Blood routine	X			X		X	X				
Biochemistry	X ^d			X		X	X				
Pregnancy(HCG/urine) ^b	X	X				X					X

Scheduled visit	1	2	3	4	5	6	7	8	9	10	11/ET	
Test & observations	Screening	1 st vaccination					2 nd vaccination				Month 3 follow-up ^g	Month 6 follow-up ^h
Day	-14~-1	0	3 ^c ±1day	7 ±1day	14 ±3days	28 ±3days	35 ±3days	42 ±3days	56 ±3days	112 ±5days	196 ±15days	
Lab (Immunogenicity)												
Humoral immune response		X			X	X		X	X	X	X	
Cellular immune response		X		X		X	X				X	
Study Related Procedures												
Vaccination		X				X						
Dispense diary card ^e		X				X						
Return diary card ^e				X			X					
AEs/SAEs		X	X	X	X	X	X	X	X	X	X	
COVID-19 infection surveillance									X	X	X	
Concomitant Medication	X	X	X	X	X	X	X	X	X	X ^f	X ^f	

a: Body weight and height will be assessed at Visit 1 only.

b: Screening for pregnancy will be performed (serum β -HCG pregnancy test at screening and urine pregnancy test before vaccination on Day 0, 28 and 196, for WoCBP only). It is not required for postmenopausal or surgically sterilized women. A positive urine pregnancy test should be confirmed by a serum test. Serum pregnancy testing in lieu of urine pregnancy tests will not be considered a protocol deviation.

c: Only for first 6 subjects in each group.

d: HbA1c will be only assessed at Visit 1 only.

e: In case of e-diary, it is no dispensing or return activity.

f: Only record medication for SAE.

g: 3 months after 2nd vaccination

h: 6 months after 2nd vaccination

i: The ECG will be performed within 1 hour after vaccination.

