7.2 Schedule of Assessments

Below is a list of all study procedures through the study period and the signs “X” indicate when the procedures are performed.

Scheduled visit	1	2	3/ET
Test & observations	Booster vaccination ^d		Follow-up ^e
Day	1	15 ±3 days	85 ±5 days
Informed consent	X		
Inclusion/Exclusion Criteria	X		
Demographics	X		
Medical history	X		
Physical Exam ^a	X	X	X
Vital sign	X	X	X
Lab (Safety)			
Blood routine	X	X	
Biochemistry	X	X	
Pregnancy ^b	X		X
Lab (Immunogenicity)			
Humoral immune response	X	X	X
Cellular immune response	X	X	X
Lab (SARS-CoV-2 test)			
Serum antibodies (IgG) against SARS-CoV-2 ^f	X		X
Vaccination	X		
e-diary instruction	X		
AEs/SAEs	X	X	X
COVID-19 infection surveillance		X	X
Concomitant Medication	X	X	X ^c

a: Body weight and height will be assessed at Visit 1 only.

b: Screening for pregnancy will be performed before vaccination. It is not required for postmenopausal or surgically sterilized women. When positive urine pregnancy test is presented, it should be confirmed by a serum β-HCG test. Serum testing in lieu of urine tests will not be considered a protocol deviation.

c: Only record medication for SAE and AESI.

d: The day is at least 6 months after **completing the primary vaccination series** in V-122 study.

e: 3 months after booster vaccination.

f: Serum antibodies (IgG) against SARS-CoV-2 will be assessed by UBI SARS-CoV-2 ELISA kit.

ET: early termination

Blood collection at scheduled visits

Scheduled visit	1	2	3
Test & observations	Booster vaccination		Follow-up
Day	1	15±3	85±5
Blood volume (mL)			
Lab (Safety)			
Blood routine	4.5	4.5	
Biochemistry	2.5	2.5	
Lab (Immunogenicity)			
Humoral immune response	10	10	10
Cellular immune response	56	56	56
Lab (SARS-CoV-2 test)			
Serum antibodies (IgG) Against SARS-CoV-2	2		2
Total blood collection	75	73	68

Total amount of blood collection: 216 mL.

* If HLA genotyping will be performed, additional 3 mL of blood sample will be collected.

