b: Screening for pregnancy and proteinuria will be performed by urine sample on Day 1, Day 29. When positive urine pregnancy test is presented, it should be confirmed by a serum test. Serum testing in lieu of urine tests will not be considered a protocol deviation. Proteinuria is checked via urine routine as baseline.

c: For anti-S1-RBD IgG levels, SARS-CoV-2 neutralizing titers, and antibody titers which inhibit S1-RBD: ACE2 binding.

d: All subjects will receive safety calls that will serve both to monitor for unsolicited AEs, including AESIs, and to monitor for symptoms of COVID-19.

e: Each week (i.e., every 7 days) the subject will receive a prompt on their smartphone device to regularly surveillance for signs and symptoms of COVID-19. Record medication for potential COVID-19 on COVID-19 page.

f: Only record medications for MAAE and SAE.

g: 28 days after 2nd vaccination

h: **Only for subjects in vaccine group and have agreed to receive 3rd dose of UB-612.**

i: 12 months (336 days) after 2nd vaccination

j: Safety laboratory includes complete blood count (Hgb, Hct, RBC), WBC with differential, platelet count, creatinine, ALT, AST, total and direct bilirubin, hs-CRP, and ANA.

k: Active collection period

l: Passive surveillance period.

m: Visit 1 and 2 could be emerged as one visit.

n: Anti-S1-RBD IgG level only

o: Up to 100 aged >18-< 65 subjects in selected sites will be invited

p: To include PIMMC (listed in **Table 9-6**), or any newly identified potential AESI followed through 12 months after participants' final vaccination. Complications of COVID-19, also termed as ADE, (listed in **Table 9-5**) should be considered and reported as AESIs.

q: **If subject encountered \geq Grade 3 hypertension, the existence or deterioration of proteinuria will be checked .**

r: **An aliquot of spared serum is to be frozen and stored for UBI SARS-CoV-2 ELISA, Confirmatory SARS-CoV-2 ELISA, and future immunologic tests.**

s: **Subjects who qualified to receive 3rd dose will enter 2 weeks e-diary for follow-up and a safety call post 7 days post vaccination.**

t: **Visit 5 and Visit 6 could be the same day.**

u: **Approximately thirty aged >18-< 65 subjects and approximately thirty aged \geq 65 years subjects in selected sites will be invited. When applicable, subjects who were assessed for T cell functions on Day 57 are preferred to be invited.**

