7.5.4 Prior and Concomitant Therapy

There is no specific known evidence of contraindications between the ingredients of UB-612 vaccine and other prior and concomitant therapy. Concomitant medications and therapies will be recorded beginning 1 month prior to 1st vaccination, as well as during study period.

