7.5.4.1 Prohibited Medication/Therapy

The following medications or treatments which may affect the immunogenicity and clinical efficacy assessments will be prohibited in subjects who assess immunogenicity:

- Immunosuppressant, cytotoxic treatment until Day 197
- Immunoglobulins and/or any blood products until Day 197
- Systemic corticosteroids (≥ 20 mg/day of prednisone or equivalent) until Day 197
- Investigational product (including drug, vaccine) during study period
- Any seasonal or pandemic influenza vaccine within 14 days, or any other nonstudy vaccine within 28 days, after study intervention administration. Licensed COVID-19 vaccine is prohibited through the whole study period.

The following medications or treatments which may affect the immunogenicity and clinical efficacy assessments will be prohibited in subjects who assess safety only:

- Immunosuppressant, cytotoxic treatment until Day 57
- Immunoglobulins and/or any blood products until Day 57
- Systemic corticosteroids (≥ 20 mg/day of prednisone or equivalent) until Day 57
- Investigational product (including drug, vaccine) during study period
- Any seasonal or pandemic influenza vaccine within 14 days, or any other nonstudy vaccine within 28 days, after study intervention administration. Licensed COVID-19 vaccine is prohibited through the whole study period.

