8.1.13 Long-term follow-up (Day 365 \pm 45 days)

(1) Measure vital signs.

(2) If subject encountered \geq Grade 3 hypertension, subject should be checked the existence or deterioration of proteinuria or other renal damage sign.

(3) Collect blood sample for following tests only for subjects **have 2 vaccinations** in lot-to-lot consistency /immunogenicity group:

- Immune response assessments

(4) Collect blood sample for following tests only for subjects have 3rd vaccination:

- Immune response assessments

- (5) Record adverse events, including AESI, MAAE, SAE, or any symptoms of COVID-19 if any has occurred since the previous visit.

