10.3 Analysis Populations

Enrolled Population

Enrolled Population includes subjects who have a signed ICF.

Randomized Population

Subjects who are assigned a random number be regarded as Randomized Population.

Evaluable Immunogenicity Population

Evaluable Immunogenicity Population will consist of all eligible randomized subjects who are assigned to lot-to-lot and immunogenicity group, receive two vaccinations within the predefined window, have a valid immunogenicity result at visit 4 (Day 57), have no major protocol deviations or protocol deviations having impact on immunogenicity data. Evaluable Immunogenicity Population will be regarded as primary population for immunogenicity evaluation on primary and secondary immunogenicity endpoints except lot-to-lot consistency.

Evaluable Lot-to-Lot Population

Evaluable Lot-to-Lot Population is a subset of Evaluable Immunogenicity but only includes subjects who are assigned to lot-to-lot consistency group and have immunogenicity determination at Day 57. Evaluable Lot-to-Lot Population will be used for evaluating lot-to-lot consistency only.

Evaluable Efficacy Population

All eligible randomized subjects who receive two vaccinations within the predefined window and have no major protocol deviations or protocol deviations having impact on immunogenicity data will be the Evaluable Efficacy Population. Evaluable Efficacy Population will be used to evaluate vaccine efficacy in exploratory analysis.

Available Immunogenicity Population

Available Immunogenicity Population will consist of all eligible randomized subjects who receive at least one vaccination, and have at least one post immunogenicity data determination. Available Immunogenicity Population will also be used to the immunogenicity evaluation except lot-to-lot consistency.

Evaluable Booster Population

All eligible randomized subjects who receive third dose of UB-612 within the predefined window and have no major protocol deviations or protocol deviations having impact on immunogenicity data will be the Evaluable Booster Population. Evaluable Booster

Population will be used to explore the immunogenicity evaluation after the booster vaccination.**Safety Population**

Safety Population (SAF) will consist of all subjects who received at least one vaccination. The Safety Population is for safety evaluation in analysis.

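### V-205 forbids outside COVID-19 vaccines for the whole study, but its medication-recording rules conflict at Visits 5 to 7 and schedule no review from Day 253 to Day 365, so boosted late titers may go undetected

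*Supplement*

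**What the plan says.** All references are to V-205 unless another protocol is named.

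- **Prohibition (7.5.4.1).** "Licensed COVID-19 vaccine is prohibited through the whole study period". This applies to the immunogenicity and safety-only subjects alike. Investigational products, vaccines included, are also barred during the study. For immunogenicity subjects the bar on immunomodulators is shorter, for example "Immunosuppressant, cytotoxic treatment until Day 197".
- **Schedule (7.2).** The concomitant-medication row is unrestricted on Days 1, 29 and 57. At Visits 5, 6 and 7 it carries footnote f in the lot-to-lot and immunogenicity table: "Only record medications for MAAE and SAE". Footnote e in the safety-check table has the same content. The row is empty on Days 253, 309 and 365.
- **General rule (7.5.4).** "Concomitant medications and therapies will be recorded beginning 1 month prior to 1st vaccination, as well as during study period".
- **Visit lists.** Sections 8.1.8, 8.1.9 and 8.1.11 (Visits 5, 6 and 7) each call for a review of concomitant medication without restriction. Section 8.1.12 limits the Day 253 and Day 309 calls to unsolicited adverse events and COVID-19 symptoms. For Day 365, section 8.1.13 asks the site to "Record adverse events, including AESI, MAAE, SAE, or any symptoms of COVID-19 if any has occurred since the previous visit" and lists no medication review.
- **Exclusions.** Section 7.4.8.1 allows a subject to be removed from the immunogenicity analysis after a prohibited product that interferes with it. Section 10.3 limits the Evaluable Immunogenicity Population to subjects who "have no major protocol deviations or protocol deviations having impact on immunogenicity data".
- **Endpoints (6.4, 10.6.2).** Day 197 and Day 365 GMT and GMFI of neutralizing and anti-S1-RBD antibody are secondary. Section 10.6.2 separates two-dose from three-dose subjects at Day 365.

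**The concern.** A prohibition protects an endpoint only if breaches are found. An uneventful vaccination at a public clinic treats no adverse event, so a site that follows the schedule footnote has no reason to record it. Nothing scheduled after Visit 7 asks about it, and for a two-dose subject nothing after Visit 5.

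An outside dose acts as a booster. Left undetected in the vaccine arm, it makes antibody persistence look better than two doses of UB-612 produced. The group most exposed is the two-dose Day 365 group: subjects who know they received UB-612 and did not take a third dose. It is plausible that some of them sought another vaccine, but the documents do not say how many.

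**Working it through.** **1. What each rule captures.** Take an outside COVID-19 vaccine with no resulting medically attended or serious event.

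| Contact | Schedule (7.2) | General rule and lists (7.5.4, 8.1) |
|---|---|---|
| Visit 5 (Day 197) | not recorded under the footnote | recorded |
| Visits 6 and 7 (third-dose takers only) | not recorded under the footnote | recorded |
| Day 253 and Day 309 calls | row empty | 7.5.4 would cover it; 8.1.12 does not ask |
| Day 365 | row empty | 7.5.4 would cover it; 8.1.13 does not ask |

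Up to Visit 7 the defect is a contradiction. After that, section 7.5.4 states a general intention with no scheduled contact to carry it out.

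**2. Length of the gaps.**

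- Day 57 to Day 197: 197 − 57 = 140 days, covered only by the Visit 5 review, whose scope is disputed.
- Two-dose subjects after Visit 5: 365 − 197 = 168 days with no scheduled medication review.
- Three-dose subjects: Visit 6 falls on Days 197 to 242, so Visit 7 is nominally on Days 211 to 256. That leaves 365 − 256 = 109 to 365 − 211 = 154 days.

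**3. Whether other procedures close the gap.** The COVID-19 page and the convalescent visit (8.4.4) are triggered by illness. The eligibility recheck before dose 3 (7.4.4.2, 9.3) would pick up another COVID-19 product, but only in third-dose takers and only up to Visit 6.

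**4. Size.** The plan states no figure to reproduce. Suppose a share c of subjects has an undetected dose that multiplies titer by r. The mean log10 titer rises by c·log10(r), so the GMT is multiplied by r^c. Both c and r are assumptions.

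| Rise r | c = 1% | c = 5% | c = 10% |
|---|---|---|---|
| 2-fold | 1.01 | 1.04 | 1.07 |
| 5-fold | 1.02 | 1.08 | 1.17 |
| 10-fold | 1.02 | 1.12 | 1.26 |

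**5. Comparison with sampling error.** Section 7.4.6 plans 696 + 132 = 828 evaluable vaccine recipients with titers. Section 10.2.2 assumes a log10 SD of 0.6. The 95% confidence factor on the GMT is 10^(1.96 × 0.6/√828) = 10^0.0409 = 1.10. With the SD of 0.223 tabulated for 100 µg neutralizing titers it is 10^(1.96 × 0.223/√828) = 1.04. The two-dose Day 365 group will be smaller than 828 by an unknown amount, so its interval will be wider.

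**The case against.** The other side has substantial points.

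- *The footnote is not the only rule.* A reader might infer that after Day 57 V-205 records nothing beyond treatment for medically attended or serious events. The documents do not support that: section 7.5.4 and the Visit 5 to 7 lists are unrestricted, COVID-19 medication goes on its own page, and the convalescent visit records prohibited products needed for care.
- *Contaminated titers need not stay in.* Sections 7.4.8.1 and 10.3 provide for removal. Source verification (11.2) or the deviation plan (10.11, not shown) may bring a breach to light. The weakness is in detection, so the titers may stay in; it is not certain that they do.
- *Immunomodulators are a weak case.* Section 9.5.6.4 defines a medically attended event broadly. Immunosuppressants, immunoglobulins or high-dose steroids started for an illness would usually fall within it and so be recorded even under the footnote. Their bar ends at Day 197, so later use breaks no rule. Immunosuppressants would tend to lower titers.
- *The vaccine wording is not empty.* Section 7.5.4.1 also bars investigational vaccines. What remains unclear is a product used under emergency authorization, which V-123 section 5.2 describes as the basis of current campaigns.
- *Loss of Day 57 results is an inference.* Section 10.3 defines the population by subject. From this a reader might conclude that a late outside vaccine deletes a valid Day 57 primary result. The analysis plan is not shown, and section 10.1 leaves full analysis detail to it, so it may handle this by time point.
- *Placebo.* Contamination there would narrow the Day 197 contrast, which is conservative. Section 8.1.8 withdraws placebo subjects at Visit 5, so none are planned at Day 365.

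These points narrow the concern. They do not supply a medication or vaccine question between Visit 5 and Day 365 for two-dose subjects, and they do not settle which rule governs Visits 5 to 7. An analysis plan cannot recover data that were never collected.

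**Conclusion.** The point stands in limited form. The recording footnotes contradict section 7.5.4 and the Visit 5 to 7 lists, and no medication or vaccine review is scheduled on Days 253, 309 or 365. An uneventful outside COVID-19 vaccination may therefore go undetected, and the exclusions cannot act on it. The Day 197 and especially the two-dose Day 365 secondary GMT and GMFI may then overstate persistence.

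The size depends wholly on assumed uptake and rise. At 1% uptake with up to a 10-fold rise the inflation is at most 1.02 and negligible. At 5 to 10% uptake with a 5- to 10-fold rise it is 1.08 to 1.26, roughly equal to or larger than the sampling error of about 1.10 at n = 828 and SD 0.6. The primary Day 57 titers are not affected by the gap: recording is unrestricted up to that visit.

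**What to change.** 1. Reconcile footnote f, and footnote e of the safety-check table, with section 7.5.4 and the Visit 5 to 7 lists.
2. In section 7.2 and the matching parts of section 8.1, ask at Visits 5, 6 and 7, at the later safety calls and at Day 365 about any non-study COVID-19 vaccine, with product and date and whether licensed or under emergency authorization. Ask also about any section 7.5.4.1 product while it is prohibited. Record both whether or not they are linked to a medically attended or serious event.
3. Word the COVID-19 vaccine item in section 7.5.4.1 so that its coverage of products under emergency authorization is explicit, as the V-123 list in its section 7.5.4.1 does.
4. State in the analysis section or analysis plan that titers from the date of an outside COVID-19 vaccine onward are excluded and that earlier results, Day 57 included, are kept.

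The cost is one question at contacts that already take place, one eCRF field and a short analysis rule. The downside is slightly fewer late titers.

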7.3 Discussion of Study Design

The primary objectives of this study are to evaluate the immune response after full immunization. Secondary objectives are to evaluate persistence of immune response, and safety and tolerability of UB-612 vaccine to prevent SARS-CoV-2 infection up to 12 months. COVID-19 can affect anyone, and the disease can cause symptoms ranging from mild to very severe. For some other illnesses caused by respiratory viruses (such as influenza), some people may be more likely to have severe illness than others because they have characteristics or medical conditions that increase their risk. These are commonly called “risk factors.” Examples include older age or having certain underlying medical conditions. Older adults are at greatest risk of severe disease and death due to coronavirus disease 2019 (COVID-19). Globally, persons older than 65 years comprise 9% of the population, yet account for 30% to 40% of cases and more than 80% of deaths [13]. COVID-19 is a new disease. Currently there are limited data and information about the impact of many underlying medical conditions on the risk for severe illness from COVID-19. In this study design, adults of any age might be at an increased risk for severe illness from the virus that causes COVID-19 as defined who had at least one of the Charlson comorbidity index [14] category or obesity only (BMI ≥ 30 kg/m²).

Per EUA requirement issued by TFDA, the sponsor should submit the lot-to-lot consistency report to demonstrate the quality of vaccine product. Core group is designed for EUA application. Among 3850 subjects, 462 evaluable subjects aged from >18 to < 65 will be enrolled for lot-to-lot consistency. Additional 350 evaluable adult subjects will be assigned into immunogenicity study. In order to demonstrate vaccine efficacy in elderly, authority requests EUA package should include at least 600 elder subjects who received the vaccine. Thus we plan to enrol around 770 randomized subjects aged from ≥ 65 to 85 years old, in which at least 154 evaluable subjects will have immunogenicity data to compare with young adults. After completion recruitment of the core group, 385 adolescents will be randomly recruited as supplementary group to extend vaccine indication. At least 154 evaluable adolescents (allocation rate 6:1) will have immune data to compare with adults.

There are two interim reports for EUA application. The first is for safety follow up in core group, and the second is for lot-to-lot consistency. Also, an additional interim report of immunogenicity and safety in adolescents, will be submitted for indication extension.

The surveillance for COVID-19 will be conducted as part of the study. The serological evidences in case of confirmed and/or severe COVID-19 will be described for the change of antibody level in vaccinated subjects. All subjects would be included in the exploratory objectives of protective efficacy against COVID-19 if case detected.

Unblinding will be carried out when the subject in core group or supplementary group has completed Visit 5. Subjects who receive the placebo vaccine will allow to withdraw from the study.

7.4 Selection of Study Population

7.4.1 Number of Planned Subjects

In core group, around 3850 adult subjects will be randomized to receive 100 μ g UB-612 vaccine or placebo with 6:1 allocation rate. In supplementary group, around 385 adolescent subjects aged

from 12 to 18 years old will randomly receive UB-612 vaccine 100 µg or placebo with allocation rate 6:1, too.

